8.6.3 Summaries of Baseline Characteristics, Demographics, and Other Analyses

8.6.3.1 Demographic and Baseline Characteristics

The comparability of the treatment groups for each relevant characteristic will be assessed by the use of tables and/or graphs. No statistical hypothesis tests will be performed on these characteristics. The number and percentage of subjects randomized, and the primary reason for discontinuation will be displayed. Demographic variables (such as age) and baseline characteristics will be summarized by treatment either by descriptive statistics or categorical tables.

8.7 INTERIM ANALYSES

8.7.1 Efficacy Interim Analyses

There are two planned interim analyses (IA) for this study. The trial will continue irrespective of the outcome of the two interim analyses. Results will be reviewed by an eDMC.

IA1, which is the final analysis of ORR, will be performed after approximately the first 210 randomized subjects (~70% of the ITT population) are followed for two cycles of treatment or have discontinued earlier.

IA2, which is final PFS analysis and interim OS analysis, will be performed when all subjects are enrolled, and approximately 236 PFS events are observed.

For the hypothesis of OS, a Hwang-Shih-DeCani alpha-spending function with gamma parameter (-6), is used to construct group sequential boundaries to control the type I error rate. The actual boundaries will be determined from the number of deaths observed at the time of the interim analysis for the specified analysis using the alpha-spending function. The Hwang-Shih-DeCani alpha spending function, based on the gamma parameter selected (-6), is more conservative than the O'Brien-Fleming bound recommended by the FDA.

[Table 17](#) summarizes the timing, number of events and decision guidance for the PFS, OS and ORR analyses. The actual boundaries and the alpha level will be determined from the actual number of events observed at the time of the interim analysis using the corresponding alpha-spending function as well as the results of the ORR and PFS analyses (see Section 8.8).

Table 17 Decision Guidance at Each Efficacy Analysis

Analysis	Timing/Criteria for Conduct of Analysis	Testing	Value	Efficacy*
IA1 : ORR	~ 12 months after trial starts (~ 210 subjects randomized + 2 months)	ORR (Superiority): pembrolizumab in combination with SOC vs. SOC	ORR Δ bound [†] p-value (1-sided)	~ 17% ≤ 0.005
IA2: PFS analysis / Interim OS analysis	~ 20 months after trial starts (all subjects randomized and ~ 236 PFS events are observed) OS Events (anticipated): ~ 124	PFS (Superiority): pembrolizumab in combination with SOC vs. SOC	~ HR at bound p-value (1-sided)	0.75 ≤ 0.015
		OS (Superiority): pembrolizumab in combination with SOC vs. SOC	~ HR at bound p-value (1-sided)	0.57 ≤ 0.0007
Final OS analysis	~ 10 months after PFS analysis or ~ 182 OS events are observed, whichever comes first	OS (Superiority): pembrolizumab in combination with SOC vs. SOC	~ HR at bound p-value (1-sided)	0.68 ≤ 0.0048

*Values for PFS/OS assume that ORR/PFS are negative; actual values will depend on whether or not null hypotheses for ORR and PFS are rejected (see Section 8.8). [†]Δ = ORR in pembrolizumab group + SOC – ORR in SOC group, assuming ORR in SOC group is ~ 30%.
				

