
5. Bone marrow analysis for all subjects at baseline will include bone marrow morphology, IHC, and Cytogenetics by FISH panel for disease status assessment at local institution. If FISH is not available, then do standard karyotyping. An archival or newly obtained sample may be used at Screening. For subjects (selected sites ONLY) who agree to participate in the optional biomarker sub-study, freshly obtained bone marrow aspirate samples will be collected at C1D1, C2D1 and at time of discontinuation.
 
^a Note: If the subject signs the Future Biomedical Research (FBR) consent, any leftover tissues that would ordinarily be discarded at the end of the trial will be retained for FBR. A copy of the local pathology report, with subject information removed, should also be sent to the lab to accompany the biopsy specimen.
 
6. Pre-dose trough PK and anti-pembrolizumab antibody samples will be collected (Arm A only) at C1D1, C1D22, C2D15, C5D15 and every 4 pembrolizumab infusions thereafter, and 30 days after discontinuation of study drug (or until the subject starts new anti-cancer therapy). Pharmacokinetic/anti-drug antibody (PK/ADA) samples may be used to conduct additional safety analysis, if needed.
 
7. This sample should be drawn for planned analysis of the association between genetic variants in DNA and drug response. If there is either a documented law or regulation prohibiting collection, or if the IRB/IEC does not approve the collection of the sample for these purposes, then this sample will not be collected at that site. If the sample is collected, leftover extracted DNA will be stored for future biomedical research if the subject signs the FBR consent. If the planned genetic analysis is not approved, but FBR is approved and consent is given, this sample will be collected for the purpose of FBR
 
8. Patient reported outcomes (PROs) are assessed on day 1 of every 28-day cycle through Cycle 4 and then every 3 cycles (ie, Cycle 7, 10, 13, etc.) while the subject is receiving study treatment, at treatment discontinuation, and at 30 days post treatment discontinuation (post-treatment safety follow-up)
 
9. Whole blood for correlative studies should only be collected at C1D1, C2D1 and at discontinuation.
 
10. Cycle 1 treatment must be given within 3 days of randomization number assignment in IVRS/IWRS after ensuring subjects meet disease criteria through previous consultation with the Sponsor
 
11. The Pomalidomide Education and Counseling Guidance Document must be completed for all subjects and signed by a trained counselor prior to each dispensing of pomalidomide in accordance with the POMALYST REMS™/country specific risk mitigation program. A copy of this document must be maintained in the subject's records for each dispense for all countries/sites where pomalidomide is provided centrally by the Sponsor.
 
12. Investigational arm (Arm A) should have vital signs measurements on Day 1 of each cycle and on the day of pembrolizumab infusion before and immediately after each administration of the study drug. Weight measurement not required post infusion.
 
13. Disease Response Assessment by IMWG 2011 criteria, CBC with Differential, and Comprehensive blood Chemistry Panel do not need to be performed on Day 1, Cycle 1.
 
14. All subjects enrolled in this study must be able to provide an archived or newly obtained bone marrow biopsy or aspirate sample for minimal residual disease (MRD) characterization by central analysis at screening, at the time of achieving a CR and at 6 months and 1 year after achieving a CR.
 
15. On 03-JULY-2017, the US FDA placed KN183, KN185 and cohort 1 of KN023 on clinical hold based on safety data from KN183 and KN185 presented to the DMC. The FDA determined that the risks of pembrolizumab plus pomalidomide or lenalidomide outweighed any potential benefit for patients with multiple myeloma. Based on this decision, the treatment phase of KN183 and KN185 is closed effective immediately. All subjects must stop study treatment, complete the Discontinuation Visit and move into the long-term safety and survival follow-up per protocol.
 
16. After confirmed disease progression or start of new anti-myeloma therapy, the subject should be contacted approximately every 12 weeks to assess for survival status. Updated survival status may be requested by the Sponsor at any time during the course of the study. Upon Sponsor notification, all subjects who do not/will not have a scheduled study visit or study contact during the Sponsor-defined time period will be contacted for their survival status (excluding subjects who have previously recorded a death event in the collection tool).
											

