7.1.2.8.3 Timing of Disease Assessments

Antitumor activity for both treatment arms will be based on the International Myeloma Working Group response criteria (IMWG criteria [1]) and will be performed every 28-day treatment cycle regardless of study treatment delays. Refer to [Table 9](#).

Table 9 Disease Response Assessments

Indication	Assessment Frequency
rrMM	Every 28-days (~ 4 weeks) following first assessment baseline.

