Multiplicity	
The family-wise type I error rate for this study is strongly controlled at 2.5% (one-sided) for the hypothesis testing of ORR, PFS and OS. The multiplicity strategy will follow the graphical approach of Maurer and Bretz (2013) as described in Section 8.8, with 0.5%, 1.5% and 0.5% alpha allocated to the ORR, PFS and OS hypothesis, respectively.
 
For the OS hypothesis, a Hwang-Shih-DeCani alpha-spending function with the gamma parameter (-6) is constructed to implement group sequential boundaries that control the type I error rate. Further details of the interim analysis strategy can be found in Section 8.7.1

Sample Size and Power	
The planned sample size is approximately 300 subjects. The primary endpoints of the study are PFS and OS. For PFS, based on 236 events, the study has ~90.6% power to detect a hazard ratio of 0.635 (pembrolizumab in combination with SOC vs. SOC) at alpha = 1.5% (one-sided). For OS, based on 182 events, the study has ~ 80.5% power to detect a hazard ratio of 0.600 (pembrolizumab in combination with SOC vs. SOC) at alpha = 0.5% (one-sided). For ORR based on the first 210 randomized patients followed for two cycles of treatment or have discontinued earlier, the study has 88.7% power to detect a 25 percentage point increase for pembrolizumab in combination with SOC vs SOC at alpha = 0.5% (one-sided)

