8.9 Sample Size and Power Calculations

The study will randomize approximately 300 subjects in a 1:1 ratio among the two treatment arms: pembrolizumab in combination with SOC (combination therapy), and SOC (control).

With ~ 210 subjects at IA1, the study has ~ 88.7% power for detecting a 25% difference in ORR (55% vs. 30%) at 0.5% level of significance (one-sided).

IA2, the final PFS analysis of the study will be performed after approximately 236 PFS events have been observed, and this will occur ~20 months after the first subject is enrolled.

The final OS analysis of the study will be performed 10 months after the PFS analysis or after 182 deaths have been observed in the trial, whichever comes first.

For the primary endpoint PFS, the study has ~90.6% power to detect a hazard ratio of 0.635 (pembrolizumab in combination with SOC vs. SOC) at alpha = 1.5% (one-sided). The sample size calculation is based on the following assumptions: 1) progression-free survival follows an exponential distribution with a median of 4 months in the control arm (Arm B), 2) an enrollment period of 14 months and at least 6 months follow-up, 3) a yearly dropout rate of 5% and 4) ORR is negative.

For the primary endpoint OS, the study has ~80.5% power to detect a hazard ratio of 0.600 (pembrolizumab in combination with SOC vs. SOC) at alpha = 0.5% (one-sided). These calculations are based on the following assumptions: 1) OS follows an exponential distribution with a median of 12.7 months in the control arm (Arm B), 2) an enrollment period of 14 months and at least 16 months follow-up, 3) a yearly dropout rate of 2% and 4) PFS is negative.

The assumed median PFS and OS in the control arm (Arm B) are observed for standard of care in treatment of refractory or relapsed multiple myeloma [46]

The sample size and power calculations were performed in the software EAST 6.

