					Development of hypercalcemia (corrected serum calcium > 11.5 mg/dL) that can be attributed solely to the PC proliferative disorder

Adapted from Durie et al⁷ and Kyle et al¹³ with permission. All response categories (CR, sCR, VGPR, PR, and PD) require 2 consecutive assessments made at any time before the institution of any new therapy; CR, sCR, VGPR, PR, and SD categories also require no known evidence of progressive or new bone lesions if radiographic studies were performed. VGPR and CR categories require serum and urine studies regardless of whether disease at baseline was measurable on serum, urine, both, or neither. Radiographic studies are not required to satisfy these response requirements. Bone marrow assessments need not be confirmed. For PD, serum M-component increases of more than or equal to 1 g/dL are sufficient to define relapse if starting M-component is ≥ 5 g/dL.

PCs indicate plasma cells.

*Clarifications to IMWG criteria for coding CR and VGPR in patients in whom the only measurable disease is by serum FLC levels: CR in such patients indicates a normal FLC ratio of 0.26 to 1.65 in addition to CR criteria listed above. VGPR in such patients requires a > 90% decrease in the difference between involved and uninvolved FLC levels.

†Clarifications to IMWG criteria for coding PD: Bone marrow criteria for PD are to be used only in patients without measurable disease by M protein and by FLC levels; "25% increase" refers to M protein, FLC, and bone marrow results, and does not refer to bone lesions, soft tissue plasmacytomas, or hypercalcemia and the "lowest response value" does not need to be a confirmed value.

Table 2. Additional response criteria and updates

MR in patients with relapsed refractory myeloma adopted from the EBMT criteria ⁶	Immunophenotypic CR	Molecular CR
≥ 25% but ≤ 49% reduction of serum M protein and reduction in 24-hour urine M-protein by 50%-89%	Stringent CR plus	CR plus negative ASO-PCR, sensitivity 10 ⁻⁵
In addition to the above criteria, if present at baseline, 25%-49% reduction in the size of soft tissue plasmacytomas is also required	Absence of phenotypically aberrant PCs (clonal) in BM with a minimum of 1 million total BM cells analyzed by multiparametric flow cytometry (with > 4 colors)	
No increase in size or number of lytic bone lesions (development of compression fracture does not exclude response)		

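### Does the 88.7% ORR power overstate what can be confirmed at IA1, where some subjects have only two cycles of follow-up?

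*Combined protocol and SAP*

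**What the plan says.** Section 8.7.1 makes IA1 the only formal test of ORR: "IA1, which is the final analysis of ORR, will be performed after approximately the first 210 randomized subjects" (about 70% of the ITT population) "are followed for two cycles of treatment or have discontinued earlier". Table 17 places it about 12 months after the trial starts, two months after the 210th subject is randomized. The one-sided level is 0.005.

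The power statement appears twice. Section 8.1 introduces it with "For ORR based on the first 210 randomized patients followed for two cycles of treatment or have discontinued earlier" and gives 88.7% for a 25-point increase. Section 8.9 repeats it for about 210 subjects at IA1, with the rates 55% and 30%. The Table 17 footnote assumes about 30% in the control group when it gives the IA1 bound.

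Three other provisions bear on follow-up:

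- Section 7.1.2.8.3: response assessment "will be performed every 28-day treatment cycle regardless of study treatment delays".
- Trial Flow Chart, footnote 13: response assessment and certain laboratory panels "do not need to be performed on Day 1, Cycle 1", so the first scheduled response assessment on treatment is Cycle 2 Day 1.
- Section 12.7, footnote to the IMWG table: "All response categories (CR, sCR, VGPR, PR, and PD) require 2 consecutive assessments made at any time before the institution of any new therapy".

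**The concern.** Read together, these provisions leave late enrollees little room. A subject with exactly two cycles has two scheduled post-baseline assessments, Cycle 2 Day 1 and Cycle 3 Day 1. On that schedule the subject counts as a responder only if already in partial response at the first of them.

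For PFS and OS, Section 8.9 lists a distribution, accrual, follow-up and dropout. For ORR it gives only the two rates, the number of subjects and the level. The 30% lies close to the 31% and 33% that Section 4.2.2.3 cites for pomalidomide from earlier studies, with no follow-up time attached. If 30% and 55% are rates that would be reached eventually, some of those responses would not yet be confirmed at IA1. The visible difference would then be under 25 points and the power under 88.7%. At stake would be the chance of an ORR claim, and of passing the ORR alpha on under Section 8.8.

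**Working it through.** **1. The plan's own figure.** Inputs from Sections 8.1 and 8.9: 210 subjects at 1:1 (105 per arm), 55% and 30%, one-sided 0.005 (z = 2.576).

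Power = Φ(difference / SE − z), with unpooled SE = √[(0.55×0.45 + 0.30×0.70)/105] = √(0.4575/105) = 0.0660.

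0.25/0.0660 = 3.787; 3.787 − 2.576 = 1.211; Φ(1.211) = 88.7%.

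The stated figure is reproduced. (Pooled variance gives 87.0%.) The calculation uses the two rates exactly as given, so any allowance for follow-up would have to be in the rates themselves.

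**2. Follow-up at IA1.** Section 8.9 assumes 300 subjects over 14 months. With uniform accrual, 210 are enrolled by 14 × 210/300 = 9.8 months. Two cycles are 56 days, or 1.84 months, so IA1 falls at about 11.6 months, in line with Table 17. Follow-up then runs from 1.84 to 11.64 months, with a median of 6.7.

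- Only two scheduled post-baseline visits (under 12 weeks): 0.92/9.8 = 9%, about 20 subjects.
- Under 16 weeks: 1.84/9.8 = 19%, about 39 subjects.

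**3. What if the rates are eventual?** The documents give no time to response, so one must be assumed. Take it as exponential with median m months among eventual responders, the same in both arms. A subject followed for k whole cycles is counted if the response began by the end of cycle k − 1. The share counted, f, is therefore the average over subjects of 1 − 2^(−0.92(k−1)/m). Multiply both rates by f and repeat step 1. For an upper bound, let every response be confirmed the day it occurs, so that the share is the average of 1 − 2^(−t/m) over follow-up t.

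Example, m = 1: f = 0.895; the rates become 49.2% and 26.9%; the difference is 22.4 points; SE = 0.0652; Φ(3.432 − 2.576) = 80%.

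| Assumed median (months) | Share counted, scheduled visits | Difference at IA1 (points) | Power, scheduled visits | Power, immediate confirmation |
|---|---|---|---|---|
| 0.5 | 96% | 24 | 86% | 88% |
| 0.75 | 93% | 23 | 83% | 87% |
| 1 | 89% | 22 | 80% | 86% |
| 1.5 | 83% | 21 | 74% | 81% |
| 2 | 76% | 19 | 67% | 76% |

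**4. Which reading do the documents support?** Section 8.1 ties the 25-point increase to the first 210 subjects followed for two cycles or discontinued earlier. Section 8.9 ties it to the subjects at IA1, and the Table 17 footnote ties the 30% to the IA1 bound. Nowhere are the rates called eventual or best-ever.

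The cited rates do not contradict this. The planned 30% is 30/33 = 91% and 30/31 = 97% of the two control figures, close to the shares of 89% to 96% in the table for medians of 1 to 0.5 months. The triplet pilot in Section 4.2.2.2 reached 50% (11 of 22) at a median follow-up of only 16 weeks, or 3.7 months, against about 6.7 months here.

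**5. What a shortfall would touch.** Section 8.9 computes PFS power on the assumption that ORR is negative and OS power on the assumption that PFS is negative. The PFS and OS bounds in Table 17 carry the same condition. A missed ORR test therefore lowers neither the 90.6% nor the 80.5%.

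**The case for a change.** The best argument for acting is that this is the only ORR test, that nothing was deducted inside the power calculation, and that one sentence would settle the time basis. Before treatment closed, a six-cycle minimum would also have put IA1 at about 9.8 + 5.5 = 15.3 months, still ahead of the PFS analysis at about month 20 and with no added patients. Under the step 3 assumptions it would have restored power to 84% to 89%.

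Part of this stands. The time basis is not stated, and the two-cycle minimum and the confirmation rule are real. The pilot evidence is also weak support for the IA1 reading, since it rests on 22 evaluable patients and modified response criteria.

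The rest does not carry a change. The undiscounted calculation is the right one if the inputs are IA1 rates. The loss depends on an assumed time to response, and nothing in the documents favours the slow end of the range. The IMWG footnote allows the two assessments at any time, so the 28-day wait for confirmation is a feature of the visit schedule and not a rule. An earlier look against a slightly fuller response count is a choice the sponsor may make for a secondary endpoint with 0.5% alpha, in a trial that continues whatever IA1 shows.

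The longer minimum also has no effect now. Sections 1.0, 5.2.3 and 8.0 record that all subjects had to stop treatment in July 2017, so every subject meets a minimum that ends with the words on earlier discontinuation.

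**Conclusion.** The concern does not call for a change. The 88.7% is arithmetically correct and holds on the reading that Sections 8.1 and 8.9 favour, namely rates expected at the IA1 cut-off. What is missing is a descriptive detail, the time basis of the two rates. The ORR test, its level and its analysis set are fully specified without it.

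On the other reading, power would be 67% to 86% on scheduled visits and 76% to 88% with immediate confirmation. Both ranges rest on uniform accrual, exponential times to response with medians of 2 down to 0.5 months, and equal shares in both arms; the response times and equal shares are not in the documents. Even then the type I error and the stated PFS and OS power stand, and a retrospective restatement of power would alter no test or estimate. If the ORR result is discussed in the CSR, where Section 8.0 says modifications will be reported, the authors can note the follow-up behind it without amending the plan.

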8.8 Multiplicity

The multiplicity strategy specified in this section will be applied to the primary hypotheses (PFS and OS) and the secondary hypothesis (ORR) to control the overall Type-I error at 2.5% (one-sided). The graphical approach of Maurer and Bretz [59] is followed. Figure 3 provides the multiplicity strategy diagram of the trial. In this approach, when a particular null hypothesis is rejected, the arrow(s) leading to it are removed, and the Type I error allocated to the null hypothesis that was rejected is re-distributed to the other hypotheses. The arrows on the diagram show how the Type I error allocated to a hypothesis that was successfully tested will be re-distributed for the testing of the other hypotheses.

For the hypothesis of OS, a Hwang-Shih-DeCani alpha-spending function with gamma parameter (-6), is used to construct group sequential boundaries to control the type I error rate.

[figure not shown]

Figure 3 Multiplicity Strategy

8.9 Sample Size and Power Calculations

The study will randomize approximately 300 subjects in a 1:1 ratio among the two treatment arms: pembrolizumab in combination with SOC (combination therapy), and SOC (control).

With ~ 210 subjects at IA1, the study has ~ 88.7% power for detecting a 25% difference in ORR (55% vs. 30%) at 0.5% level of significance (one-sided).

IA2, the final PFS analysis of the study will be performed after approximately 236 PFS events have been observed, and this will occur ~20 months after the first subject is enrolled.

The final OS analysis of the study will be performed 10 months after the PFS analysis or after 182 deaths have been observed in the trial, whichever comes first.

For the primary endpoint PFS, the study has ~90.6% power to detect a hazard ratio of 0.635 (pembrolizumab in combination with SOC vs. SOC) at alpha = 1.5% (one-sided). The sample size calculation is based on the following assumptions: 1) progression-free survival follows an exponential distribution with a median of 4 months in the control arm (Arm B), 2) an enrollment period of 14 months and at least 6 months follow-up, 3) a yearly dropout rate of 5% and 4) ORR is negative.

For the primary endpoint OS, the study has ~80.5% power to detect a hazard ratio of 0.600 (pembrolizumab in combination with SOC vs. SOC) at alpha = 0.5% (one-sided). These calculations are based on the following assumptions: 1) OS follows an exponential distribution with a median of 12.7 months in the control arm (Arm B), 2) an enrollment period of 14 months and at least 16 months follow-up, 3) a yearly dropout rate of 2% and 4) PFS is negative.

The assumed median PFS and OS in the control arm (Arm B) are observed for standard of care in treatment of refractory or relapsed multiple myeloma [46]

The sample size and power calculations were performed in the software EAST 6.

